## 5. BACKGROUND

### 5.1. Crenolanib inhibits wild-type FLT3 and its constitutively active mutations

Crenolanib besylate (also known as AR-868,596-26) is an orally bioavailable class III RTK inhibitor that potently targets FLT3. Crenolanib inhibits wild-type FLT3, and its constitutively active mutations at clinically achievable concentrations. [4, 5]

[figure not shown]
Crenolanib has heightened binding affinity against the FLT3-ITD mutation (the most frequent FLT3 aberration in AML) and TKD point mutations FLT3 (D835H), FLT3 (D835Y) and FLT3 (D835V). Crenolanib binds to FLT3-ITD and FLT3-TKD D835H with  $K_d$  values of 0.43 and 0.4 nM, respectively. Similarly, crenolanib also binds to FLT3-TKD D835Y with a  $K_d$  of 0.18 nM. A saturation mutagenesis screen of FLT3 ITD showed that crenolanib is a “pan-FLT3 inhibitor” that has the ability to successfully suppress all resistance-conferring TKD mutants.[4] Crenolanib inhibitory activity has been verified in human AML cell lines. [4]

**Table 1 Dissociation constants of crenolanib with constitutively active FLT3 mutations**

Gene Symbol	Crenolanib $K_d$ (nM)
FLT3(ITD)	0.43
FLT3(D835H)	0.4
FLT3(D835Y)	0.18
FLT3 (D835V)	0.048

Crenolanib is a type 1 tyrosine kinase inhibitor that binds to both the active and inactive conformation of FLT3.

**Figure 1 Schematic of inactive and active FLT3 with most common resistance mutations in AML.[8]**

[figure not shown]
### 5.2. Crenolanib has reduced activity against KIT

Crenolanib has been found to be approximately 100-fold more selective for FLT3 than for KIT and is therefore highly selective toward FLT3 relative to KIT [9] and elicits cytotoxicity in FLT3-mutant AML while largely sparing KIT inhibition (100-fold offset in both viability and biochemical assays) with limited activity against other kinases. As a result, crenolanib may be associated with less myelosuppression than the available type II FLT3 TKIs.

### 5.3. Synergistic activity of crenolanib in combination with cytarabine

The effect of crenolanib on nucleoside analogue uptake in AML cells was evaluated. Cells were incubated for 2 h with 1.25 uM of radiolabeled cytarabine combined with DMSO control or in combination with crenolanib at 0.1 uM for 5 minutes and 2 h (Figure 2). Combining cytarabine with crenolanib in FLT3 wild-type OCI-AML3 cells and FLT3-ITD MV411 cells showed that crenolanib does not decrease cytarabine accumulation in AML cells, despite length of crenolanib incubation time.[5]

[figure not shown]
**Figure 2 Effects of crenolanib on uptake of cytarabine in AML cells.**

(A) 5 minute incubation; (B) 2 hour incubation. Histogram shows mean and SD.

Further combination experimentation was undertaken to give insight into the potential sequence of crenolanib and cytarabine administration in future clinical studies. Assays were performed to measure cell viability of FLT3 ITD cell lines (MOLM13 and MV4-11) that were incubated for 4 h with cytarabine followed by 68 h of crenolanib (Figure 3). Results suggested synergistic activity with the combination [5].

**Figure 3 Crenolanib and cytarabine combination synergistically inhibit FLT3-ITD-positive cell viability in vitro.**

[figure not shown]

(A) simultaneous 72 h drug exposure; (B) simultaneous 4 h drug exposure followed by 68 h crenolanib exposure; (C) (pre-AraC) 4 h AraC exposure followed by 68 h crenolanib exposure; or (D) (pre-crenolanib) 24 h crenolanib exposure followed by 48 h AraC exposure. [5].

#### 5.4. Antileukemic activity of crenolanib in combination with daunorubicin

In vitro combination studies with crenolanib and daunorubicin also suggest antileukemic synergy in AML cell lines with mutant FLT3 (Figure 4, unpublished data on file, [name]).

**Figure 4 Viability of FLT3 ITD cell lines treated with crenolanib and daunorubicin**

[figure not shown]

(A) Molm 13 cell line; (B) MV4-11 cell line

#### 5.5. Clinical studies of crenolanib in AML

##### 5.5.1. Clinical summary of crenolanib in relapsed/refractory FLT3 mutated AML

Crenolanib has been studied in relapsed/refractory FLT3 mutant AML (NCT01522469, NCT01657682). Crenolanib was administered as single-agent in 69 patients with relapsed/refractory FLT3 mutated AML in two clinical trials, NCT01522469/ARO-004 and NCT01657682/ARO-005. Encouraging single-agent activity, safety and PK was observed with crenolanib in this patient population. Amongst 18 evaluable who had relapsed AML patients after chemotherapy or allogeneic stem cell transplant (but who had not received prior FLT3 inhibitors), crenolanib therapy resulted in an overall response rate of 50% (39% CR and 11% PR). Median overall survival was almost eight months (234 days). The overall response to crenolanib monotherapy was 31% in 36 patients who progressed after a median of three prior regimens (including chemotherapy and FLT3 inhibitors like sorafenib, midostaurin and quizartinib). Crenolanib had a half-life of 7.5hrs and no crenolanib accumulation seen with repeated dosing. Common adverse events (AEs) included nausea/vomiting, transaminitis and fluid retention (majority Grade 1/2) and only 2 patients discontinued crenolanib due to related AEs (fatigue and nausea). No patient acquired a secondary FLT3 mutation at the time of relapse following crenolanib.

**Figure 5 Peripheral blast clearance in FLT3 mutant AML patients treated with crenolanib.**

In conclusion, crenolanib is a FLT3 TKI showing preliminary clinical activity in a heavily pretreated population with FLT3-ITD, FLT3-D835, and compound FLT3-ITD/D835 mutant AML. Importantly, crenolanib is the first agent to demonstrate clinical activity in patients with FLT3-D835 activating mutations.

### 5.6. Tolerability of crenolanib in AML patients who had undergone prior allogeneic bone marrow transplant

A retrospective analysis of those patients who, following hematopoietic cell transplant (HCT), received monotherapy crenolanib on the relapsed/refractory AML studies (ARO-004 and ARO-005) was performed and reported at ASH 2015. This analysis showed that crenolanib at the full therapeutic dose of 100 mg TID was well tolerated in this heavily pre-treated patient population following HCT. A phase II clinical trial of crenolanib in the post-HCT maintenance setting (NCT02400255 / ARO-009) is on-going.

### 5.7. Long-term Safety Data of Crenolanib

In a Phase I pediatric glioma study conducted at the St. Jude Children's Research Hospital, 6 children received crenolanib for at least 12 cycles. Four children have stayed on study for more than 24 cycles. No dose reduction was required. Long-term exposure to crenolanib seems to be tolerable and safe.

[figure not shown]
### 5.8. Rationale for Crenolanib Dose and Schedule

Crenolanib has been tested in 51 AML patients as single agent. Two dosing schedules have been studied: 100 mg TID (28 patients) and 200 mg/m^2/day (23 patients). Crenolanib was safe and well tolerated in this patient population. The most common adverse events were low-grade nausea, vomiting, diarrhea, and transaminitis.

To date, 28 AML patients have been treated with 100 mg TID crenolanib. Day 1 pharmacokinetics data is shown in Figure 6. Trough crenolanib levels were measured in 25 patients on Day 15 by which time steady state levels should have been achieved. Only 2 patients had > 1000 nM crenolanib, but neither required dose de-escalation due to adverse events. Thus, a fixed dose

[figure not shown]
regimen of 100 mg TID will be utilized for this trial. Dose reductions to 80 mg TID and 60 mg TID will be applied should toxicities emerge in study individuals.

**Figure 6 Pharmacokinetics analyses in AML patients on 100 mg crenolanib.**

Previous plasma inhibitory assays have shown that FLT3 phosphorylation is inhibited for approximately 8 hours after each dose of crenolanib (see representative PIA assay below in Figure 7). Hence, crenolanib will be given in this protocol in a TID schedule.

**Figure 7 Representative PIA analysis of patient plasma samples after taking crenolanib single agent.**

The study by Robert J. et al. in 16 leukemia patients showed that the major metabolites of idarubicin or daunorubicin were the 13-dihydroderivative of each drug, idarubicinol or daunorubicinol. The elimination half-life of idarubicinol was two times higher than that of daunorubicinol (80.7 h versus 37.3 h). [6] During 7+3 induction in this protocol, idarubicin or daunorubicin will be administered on days 1, 2, and 3. By the time crenolanib is started (Day 9), idarubicinol level should have declined by 75% (2 half-lives) and daunorubicinol levels will have dropped by 93.5% (4 half-lives). Crenolanib will be discontinued 3 days (9 half-lives) prior to initiation of subsequent chemotherapy.

## 6. STUDY OBJECTIVES

### 6.1. Primary Objective

- To determine the safety and tolerability of crenolanib given sequentially with cytarabine and anthracycline chemotherapy for newly diagnosed FLT3 mutant AML.
- To determine the response rate to induction therapy in newly diagnosed AML subjects with FLT3 activating mutations when crenolanib is given sequentially with standard induction/consolidation chemotherapy, including the rates of complete remission (CR), CR with incomplete blood count recovery (CRi) and partial remission (PR).

### 6.2. Secondary Objectives

- To determine the overall survival (OS) in newly diagnosed AML subjects with FLT3 activating mutations when crenolanib is given sequentially with standard induction/consolidation chemotherapy
- In those patients achieving response with crenolanib, assess parameters of response including remission duration and relapse-free survival (RFS)
- Pharmacokinetic analysis of crenolanib when given with chemotherapy

### 6.3. Exploratory Objectives

To evaluate the impact of crenolanib given in combination with chemotherapy:

- Determine steady-state serum crenolanib concentration
- Identify and correlate specific molecular markers with clinical outcomes
- Determine changes in molecular markers during treatment and their correlations with clinical outcomes
- Measure minimal residual disease (MRD) and correlate with post-remission outcomes

## 7. SUBJECT ELIGIBILITY

All patients must meet eligibility as defined. Clarifications of eligibility should be directed to the sponsor's medical monitor.

### 7.1. Inclusion Criteria

1. Unequivocal diagnosis of AML based on WHO classification, excluding acute promyelocytic leukemia.
2. No prior therapy for AML, except for hydroxyurea and/or leukapheresis, in this setting is allowed.
3. Subjects with AML evolving from MDS with or without prior MDS therapy with demethylating agents will be allowed in the **safety phase only**.
4. Subjects must have tested positive for FLT3-ITD and/or other FLT3 activating mutations.
5. Age  $\geq 18$  years will be allowed in the **safety phase**; during the **expansion phase**, subjects must be  $\geq 18 - \leq 70$  years of age.
6. ECOG PS 0 – 2
7. Adequate liver function, defined as normal bilirubin, ALT  $\leq 2.0 \times$  ULN, and AST  $\leq 2.0 \times$  ULN measured within 24 hours prior to crenolanib commencement.
8. Adequate renal function, defined as serum creatinine  $\leq 1.5 \times$  ULN or GFR  $> 50$  mL/min
9. Negative pregnancy test (serum or urine) for women of childbearing potential (WOCBP).
  - Women considered not of childbearing potential include any of the following: no menses for at least 2 years or menses within 2 years but amenorrheic for at least 2 months and luteinizing hormone (LH) and follicular stimulating hormone (FSH) values within normal range (according to definition of postmenopausal for laboratory used) or bilateral oophorectomy or radiation castration and amenorrheic for at least 3 months or with bilateral tubal ligation.
10. WOCBP must practice contraception. Acceptable methods of contraception are double barrier methods (condoms with spermicidal jelly or foam and diaphragm with spermicidal jelly or foam), oral, depo provera, or injectable contraceptives, intrauterine devices, tubal ligations, and abstention.
11. Male patients (except those with prior surgical contraceptive procedures) with female partners who are of childbearing potential: Recommendation is for male and partner to use effective contraceptive methods, such as latex condoms, during the study.
12. Able and willing to provide written informed consent.

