#### Inclusion Criteria:

1. Unequivocal diagnosis of AML based on the WHO classification, excluding acute promyelocytic leukemia
2. No prior therapy for AML, except for hydroxyurea and/or leukapheresis, in this setting is allowed.
3. Subjects with AML evolving from MDS with or without prior MDS therapy with demethylating agents will be allowed in the safety phase only.
4. Subjects must have tested positive for FLT3-ITD and/or other FLT3 activating mutations.
5. Age  $\geq 18$  years will be allowed in the safety phase; during the expansion phase, subjects must be  $\geq 18 - \leq 70$  years of age.

6. ECOG PS 0 – 2
7. Adequate liver function, defined as normal total bilirubin, ALT  $\leq 2.0 \times$  ULN, and AST  $\leq 2.0 \times$  ULN.
8. Adequate renal function, defined as serum creatinine  $\leq 1.5 \times$  ULN or GFR  $> 50 \text{ mL/min}$
9. Negative pregnancy test (serum or urine) for women of childbearing potential (WOCBP).
  - Women considered not of childbearing potential include any of the following: no menses for at least 2 years or menses within 2 years but amenorrheic for at least 2 months and luteinizing hormone (LH) and follicular stimulating hormone (FSH) values within normal range (according to definition of postmenopausal for laboratory used) or bilateral oophorectomy or radiation castration and amenorrheic for at least 3 months or with bilateral tubal ligation.
10. WOCBP must practice contraception. Acceptable methods of contraception are double barrier methods (condoms with spermicidal jelly or foam and diaphragm with spermicidal jelly or foam), oral, depo provera, or injectable contraceptives, intrauterine devices, tubal ligations, and abstention.
11. Male patients (except those with prior surgical contraceptive procedures) with female partners who are of childbearing potential: Recommendation is for male and partner to use effective contraceptive methods, such as latex condoms, during the study.
12. Able and willing to provide written informed consent

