### **7.3. Protocol Registration**

To register, a form 1572 listed physician involved in the care of the potential participant must contact either the Principal Investigator or the Study Coordinator to complete the Eligibility Checklist for the Sponsor (Appendix I). For registration, a completed Checklist is to be provided to the sponsor who will provide the site with a Confirmation of Enrollment form which will assign a patient study number (UPIN).

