### **7.4. Discontinuations**

#### **7.4.1. Discontinuations of Study Drugs and Disease status/Survival Follow up of Patients**

The criteria for enrollment must be followed explicitly. If a patient who does not meet enrollment criteria is inadvertently enrolled, that patient should be immediately discontinued from the study drug.

Study drug may be held for an extended period of time for comorbidities including but not limited to infections, ICU admissions, severe graft vs host disease, and other comorbidities typically seen in patients undergoing induction, consolidation or allogeneic transplant therapies for AML. Such prolonged drug hold will not require the patient to be taken off study. Study drug can be restarted, even after prolonged drug holds, at the same dose as was last received by the patient. Restart of study drug will require a discussion with the sponsor.

Study drug may be held for an extended period of time if requested by the patient without necessitating the patient to be taken off study. Study drug can be restarted, even after prolonged drug holds, at the same dose as was last received by the patient. Patients will be continued to be followed for survival and disease status per protocol. Safety will be followed as per section 14.

Patients, who for any reason, require treatment with another therapeutic agent for AML or investigational agent will be discontinued from the study drug prior to introduction of the new agent. Restart of study drug will require a discussion with the sponsor.

Patients who have disease refractory to induction or consolidation therapy will be taken off crenolanib but be followed for survival. Similarly, patients who relapse after achieving a response will be taken off crenolanib but be followed for survival.

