### 10.1. Screening

The following assessments will be performed after completion of the informed consent and within 28 days of enrollment except as otherwise specified. Any test or procedure performed as per standard of care can be used for screening purposes as long as done within the window required.

1. Medical history and physical exam (includes documentation of current medications, prior relevant surgeries or treatments, allergies and prior or existing relevant medical conditions)
2. Height, weight, vital signs
3. Demographics
4. ECOG Performance Status (Appendix II)
5. Serum or urine pregnancy test for women of child bearing capacity (within 7 days of enrollment)
6. Chemistry panel including creatinine, total bilirubin, ALT, and AST (within 7 days of enrollment)
7. CBC with differential (within 7 days of enrollment)
8. Bone marrow aspirate and biopsy (within 21 days of enrollment).
9. Evaluation of FLT3-D835, FLT3-ITD and other mutational status (within 21 days of enrollment).

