#### **III. Inclusion/Exclusion Criteria**

Inclusion Criteria (From IRB approved protocol)	Yes	No	N/A	Supporting Documentation*
1. Unequivocal diagnosis of AML based on the WHO classification, excluding acute promyelocytic leukemia.				
2. No prior therapy for AML, except for hydroxyurea and/or leukapheresis, in this setting is allowed.				
3. Subjects with AML evolving from MDS with or without prior MDS therapy with demethylating agents will be allowed in the safety phase only .				
4. Subjects must have tested positive for FLT3-ITD and/or other FLT3 activating mutations.				
5. Age $\geq 18$ years will be allowed in the safety phase ; during the expansion phase , subjects must be $\geq 18 - \leq 70$ years of age.				
6. ECOG PS 0 – 2				
7. Adequate liver function, defined as normal bilirubin, ALT $\leq 2.0 \times$ ULN, and AST $\leq 2.0 \times$ ULN measured within 24 hours prior to the induction chemotherapy.				
8. Adequate renal function, defined as serum creatinine $\leq 1.5 \times$ ULN or GFR $> 50$ mL/min				

9. Negative pregnancy test (serum or urine) for women of childbearing potential (WOCBP). 
 
• Women considered not of childbearing potential include any of the following: no menses for at least 2 years or menses within 2 years but amenorrheic for at least 2 months and luteinizing hormone (LH) and follicular stimulating hormone (FSH) values within normal range (according to definition of postmenopausal for laboratory used) or bilateral oophorectomy or radiation castration and amenorrheic for at least 3 months or with bilateral tubal ligation.
 
				
10. WOCBP must practice contraception. Acceptable methods of contraception are double barrier methods (condoms with spermicidal jelly or foam and diaphragm with spermicidal jelly or foam), oral, depo provera, or injectable contraceptives, intrauterine devices, tubal ligations, and abstention.				
11. Male patients (except those with prior surgical contraceptive procedures) with female partners who are of childbearing potential: Recommendation is for male and partner to use effective contraceptive methods, such as latex condoms, during the study.				
12. Able and willing to provide written informed consent.				
Exclusion Criteria (From IRB approved protocol)	Yes	No	N/A	Supporting Documentation*

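### Liver criterion 7 is timed before crenolanib in Section 7.1 but before induction in the Appendix I checklist, and nothing says which result decides enrollment

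*Combined protocol and SAP*

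**What the plan says.** The limits agree throughout: normal bilirubin, with ALT and AST no higher than 2.0 times ULN. The timing does not.

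- Section 3.2 (synopsis), criterion 7, opens "Adequate liver function, defined as normal total bilirubin, ALT" and gives no time.
- Section 7.1, criterion 7: "measured within 24 hours prior to crenolanib commencement".
- Appendix I checklist, criterion 7: "measured within 24 hours prior to the induction chemotherapy".
- Section 10.1 lists, as a screening procedure, "Chemistry panel including creatinine, total bilirubin, ALT, and AST (within 7 days of enrollment".

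Section 7.3 makes the checklist the registration document: "For registration, a completed Checklist is to be provided to the sponsor who will provide the site with a Confirmation of Enrollment form". Section 5.8 gives the planned start of study drug: "By the time crenolanib is started (Day 9".

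Section 10.2 asks for criterion 7.1.7 to be confirmed again on the first day of crenolanib; a patient outside the limits waits until they are met. Sections 1 and 8.2.1 give the same delay rule. The consolidation key in Appendix IV calls the pre-crenolanib check a matter of eligibility.

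On patients enrolled in error, Section 7.4.1 says: "If a patient who does not meet enrollment criteria is inadvertently enrolled, that patient should be immediately discontinued from the study drug". For doubtful cases, Section 7 says "Clarifications of eligibility should be directed to" the sponsor's medical monitor.

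On the response analysis, Section 13.3.2 counts only patients who have taken study drug and had a marrow evaluated after it was planned to judge disease; Section 12.1 likewise defines responders among those receiving study drug.

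**The concern.** One numbered inclusion criterion exists in two versions that call for samples from different stages of treatment, one before the chemotherapy course and one after it. The version in the body of the protocol depends on a measurement that does not yet exist when a patient is registered before induction. The version on the form can be completed at that point but has no support elsewhere in the text.

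At stake is whether eligibility means the same thing at every site. For some patients the two texts give opposite answers, so an auditor could record a deviation under one and none under the other. The liver check also bears on who is dosed, and Section 13.3.2 makes dosing a condition for counting in the response rate. That second matter is an analysis-set question in its own right. Aligning criterion 7 would not resolve it.

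**Working it through.** No sample-size, power or error-rate figure depends on criterion 7, so the check is a comparison of texts plus a count of days.

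**Distance between the two windows.** Inputs: cytarabine runs on Days 1 to 7 (Tables 2 and 3); crenolanib starts about 24 to 48 hours after it ends, with a +7-day window (Sections 1 and 8.2.1).

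- End of cytarabine: 7 × 24 = hour 168.
- Earliest start: 168 + 24 = hour 192, the start of Day 9, which matches Section 5.8.
- Latest start without the window: 168 + 48 = hour 216, the start of Day 10.
- Gap from Day 1: 9 − 1 = 8 days, or 10 − 1 = 9 days.
- With the +7-day window: Day 16 or 17, a gap of 15 or 16 days. No maximum is stated, because going past Day 16 only calls for a discussion with the sponsor.

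**What each text does with particular patients.**

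- *Registered before induction.* Section 7.1 cannot be certified, since its sample lies at least 8 days ahead. The checklist can be, if there is a panel from the last 24 hours. A panel 2 to 7 days old satisfies the Section 10.1 window (7 × 24 = 168 hours) but not the checklist.
- *Screened during induction*, which the Appendix IV induction key contemplates. There may be no panel in the checklist window. The key lets the sponsor request pre-induction results obtained as standard of care, but does not make them the criterion.
- *Abnormal before induction, normal by about Day 9.* Eligible under Section 7.1, ineligible under the checklist.
- *Normal at both times, with both panels drawn in their windows.* Satisfies both texts.

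**What Section 10.2 settles.** It fixes the consequence of abnormal values at the planned first dose: delay. Confirming something again presupposes that it was confirmed before, and the Section 10.1 chemistry is the natural earlier check. But Section 10.2 refers back to 7.1.7, whose only stated time is the pre-crenolanib one. Dosing is therefore settled and enrollment is not.

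**Response denominator (separate).** The documents do not say how many enrolled patients will go undosed or unassessed. Let *f* be that fraction, an assumption. If the rate among dosed and assessed patients is 90% (the projection in Section 13.1.2), the rate over all enrolled, counting the others as non-responders, is 0.90 × (1 − *f*):

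- *f* = 2%: 0.90 × 0.98 = 88.2%
- *f* = 5%: 0.90 × 0.95 = 85.5%
- *f* = 10%: 0.90 × 0.90 = 81.0%

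These figures illustrate the direction and possible size; they are not estimates for this trial.

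**The case against.** The strongest reply is that this is a copying error in one form. Section 7 requires patients to meet eligibility as set out there, and the Appendix I table presents its criteria as taken from the IRB-approved protocol. Sections 1, 8.2.1 and 10.2 all agree with 7.1 on the pre-crenolanib check. The sponsor reviews each checklist before confirming enrollment, and the medical monitor can rule on doubtful cases. Most of this stands, and it makes inconsistent application less likely. It does not close the point: if 7.1 is taken as the true criterion, it still cannot be verified at a registration that precedes induction.

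A reader might go further than the documents allow in three ways.

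- *That Section 10.1 is a third conflicting timing.* It is a screening window, and it fits with a later recheck under Section 10.2. It differs from the checklist in length, but it is not a rival version of criterion 7.
- *That failing the checklist leads to discontinuation under Section 7.4.1.* The first consequence is that the patient is not registered. Section 7.4.1 applies only to someone enrolled by mistake.
- *That liver safety at first dose is exposed.* The pre-crenolanib check applies whichever text governs enrollment.

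On the response rate, it is fair to say that Section 13.1 leaves analysis detail to a separate SAP, which may define the denominator. No such SAP is among the documents, so Section 13.3.2 is the rule that can be read.

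**Conclusion.** The inconsistency is real but narrow. Criterion 7 has two incompatible timings, 8 to 9 days apart on the planned schedule and 15 to 16 days apart at the end of the start window, and no text says which result decides enrollment. The day counts assume cytarabine begins on Day 1 and runs without interruption. The number of patients with discordant results is not given, so neither a count nor a shift in response rate can be attributed to it. It is an inconsistency of conduct that should be corrected.

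The denominator point stands by itself. Section 13.3.2 names overall response as the expansion-phase endpoint but words its inclusion condition for the complete response rate; I take the condition to cover the response analysis generally. Leaving out patients who were never dosed or never assessed can only raise the rate relative to one that counts them as non-responders.

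A reader might infer from Section 13.8, which makes all subjects evaluable for safety, that undosed patients are at least fully covered there. They are not: Sections 13.8 and 14.5 leave most events before the first dose unrecorded, and Section 13.3.1 bases expansion-phase monitoring on patients who have taken study drug.

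**What to change.** Split criterion 7 in two.

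- **Enrollment criterion.** Base it on the screening chemistry within 7 days of enrollment that Section 10.1 already requires, with identical wording in Sections 3.2 and 7.1 and Appendix I. A patient screened during induction is then judged on that same screening panel.
- **Dosing condition.** Keep the 24-hour pre-crenolanib check, and label it as a dosing condition with delay as its consequence in Sections 7.1 and 10.2 and the Appendix IV consolidation key. Sections 1 and 8.2.1 already say this and need no change.

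The cost is a handful of wording edits and one real trade-off: some patients abnormal at screening who would be normal by Day 9, whom Section 7.1 now admits, would not be enrolled. Their number is unknown.

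Separately, report the response rate with all enrolled patients in the denominator, counting those never dosed or never assessed as non-responders, beside the rate defined in Section 13.3.2. That costs one table and possibly a lower figure.
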